# 6.1.6 Management of Cardiac Toxicities

Cardiac Investigations					
Electrocardiogram QT corrected (QTc) interval prolonged					
Grade 1 (QTc 450-480 ms)	Maintain dose level.				
Grade 2 (QTc 481-500 ms)	Maintain dose level.				
Grade 3 (QTc $\geq$ 501 ms on at least two	Omit EGF816 and gefitinib until QTc is less than				
separate ECGs)	481 ms and then decrease EGF816 by one dose				
	level; monitor QTc after 48 hours and 1 week on				
	EGF816, if it remains $\leq$ grade 1 after 7 days of				
	EGF816, resume gefitinib with one level dose-				
	reduction and continue to monitor QTc closely.				
	- Perform an analysis of serum potassium and, if				
	below lower limit of normal, correct with				
	supplements to within normal limits Repeat				
	ECG in 24 hours, or less, as clinically indicated;				
	continue monitoring as clinically indicated until QTc <481 ms				
	- Repeat ECGs 7 days after dose resumption for				
	all patients who had therapy interrupted due to				
	$QTc \ge 501$ ms.				
Bradycardia					
Grade 1 or 2	Omit EGF816 until recovery to asymptomatic				
	bradycardia or to a heart rate $\geq 60$ bpm. Continue				
	gefitinib.				
	Evaluate concomitant medications known to				
	cause bradycardia and adjust the dose of EGF816				
Grade 3 or	Omit EGF816 and gefitinib until recovery to				
Grade 4 (in patients taking a concomitant	asymptomatic bradycardia or to a heart rate $\geq 60$				
medication also known to cause bradycardia or	bpm				
a medication known to cause hypotension)	If grade with a concomitant medication if the				
	concomitant medication can be adjusted or				
	discontinued, resume EGF816 with a decrease by				
	one dose level with frequent monitoring, if no				
	recurrent bradycardia after 7 days on treatment,				
	resume gefitinib.				

Grade 4 (in patients who are not taking a	Permanently discontinue EGF816. If bradycardia
concomitant medication also known to cause	resolved, continue gefitinib.
bradycardia or known to cause hypotension)	

#### 7. ADVERSE EVENTS: LIST AND REPORTING REQUIREMENTS

Adverse event (AE) monitoring and reporting is a routine part of every clinical trial. The following list of reported and/or potential AEs (Section 7.1) and the characteristics of an observed AE (Section 7.2) will determine whether the event requires expedited reporting in addition to routine reporting.

#### 7.1 Adverse Event Characteristics

#### **Expected Adverse Events**

Adverse events can be 'Expected' or 'Unexpected'. Expected adverse events are those that have been previously identified as resulting from administration of the agent. For the purposes of this study, an adverse event is considered expected when it appears in the Investigator's Brochure

#### **Unexpected Adverse Events**

For the purposes of this study, an adverse event is considered unexpected when it varies in nature, intensity or frequency from information provided in the Investigator's Brochure.

• **CTCAE term (AE description) and grade:** The descriptions and grading scales found in the revised NCI Common Terminology Criteria for Adverse Events (CTCAE) version 4.0 will be utilized for AE reporting. All appropriate treatment areas should have access to a copy of the CTCAE version 4.0. A copy of the CTCAE version 4.0 can be downloaded from the CTEP web site http://ctep.cancer.gov/protocolDevelopment/electronic\_applications/ctc.htm.

• For expedited reporting purposes only:

- AEs for the agent(s) that are listed above should be reported only if the adverse event varies in nature, intensity or frequency from the expected toxicity information which is provided.
- Other AEs for the protocol that do not require expedited reporting are outlined in the next section (Expedited Adverse Event Reporting) under the sub-heading of Protocol-Specific Expedited Adverse Event Reporting Exclusions.
- **Attribution** of the AE:
  - Definite The AE is clearly related to the study treatment.
  - Probable The AE *is likely related* to the study treatment.

- Possible The AE may be related to the study treatment.
- Unlikely The AE is doubtfully related to the study treatment.
- Unrelated The AE is clearly NOT related to the study treatment.

# 7.2 Expedited Adverse Event Reporting

A serious adverse event (SAE) is any adverse event, occurring at any dose and regardless of causality that:

- Results in death
- Is life-threatening. Life-threatening means that the person was at immediate risk of death from the reaction as it occurred, i.e., it does not include a reaction which hypothetically might have caused death had it occurred in a more severe form.
- Requires or prolongs inpatient hospitalization (i.e., the event required at least a 24-hour hospitalization or prolonged a hospitalization beyond the expected length of stay). Hospitalization admissions and/or surgical operations scheduled to occur during the study period, but planned prior to study entry are not considered SAEs if the illness or disease existed before the person was enrolled in the trial, provided that it did not deteriorate in an unexpected manner during the trial (e.g., surgery performed earlier than planned).
- Results in persistent or significant disability/incapacity. Disability is defined as a substantial disruption of a person's ability to conduct normal life functions.
- Is a congenital anomaly or birth defect; or
- Is an important medical event when, based upon appropriate medical judgment, it may jeopardize the participant and require medical or surgical intervention to prevent one of the outcomes listed above. Examples of such medical events include allergic bronchospasm requiring intensive treatment in an emergency room or at home; blood dyscrasias or convulsions that do not result in inpatient hospitalization, or the development of drug dependency or drug abuse.

Events not considered to be serious adverse events are hospitalizations for:

- routine treatment or monitoring of the studied indication, not associated with any deterioration in condition, or for elective procedures
- Abnormal lab values that do not require treatment
- treatment planned before signing informed consent for a pre-existing condition that did not worsen
- emergency outpatient treatment for an event not fulfilling the serious criteria outlined above and not resulting in inpatient admission
- respite care
  - 7.2.1 Investigators **must** report to the Overall PI any serious adverse event (SAE) that occurs after the initial dose of study treatment, during treatment, or within 30 days of the last dose of treatment on the local institutional SAE form.

## 7.2.2 DF/HCC Expedited Reporting Guidelines

Investigative sites within DF/HCC will report AEs directly to the DFCI Office for

Human Research Studies (OHRS) per the DFCI IRB reporting policy.

# 7.2.3 Reporting to Novartis

To ensure patient safety, every SAE, regardless of suspected causality, occurring after the patient has provided the main informed consent and until at least 30 days after the patient has stopped study treatment must be reported to Novartis within 24 hours of learning of its occurrence. Any SAEs experienced after this 30 days period should only be reported to Novartis if the investigator suspects a causal relationship to the study treatment. Recurrent episodes, complications, or progression of the initial SAE must be reported as follow-up to the original episode within 24 hours of the investigator receiving the follow-up information. An SAE occurring at a different time interval or otherwise considered completely unrelated to a previously reported one should be reported separately as a new event.

Information about all SAEs is collected and recorded on the Serious Adverse Event Report Form; all applicable sections of the form must be completed in order to provide a clinically thorough report. The investigator must assess and record the relationship of each SAE to each specific study treatment (if there is more than one study treatment), complete the SAE Report Form in English, and send the completed, signed form by fax within 24 hours to the oncology Novartis Drug Safety and Epidemiology (DS&E) department - [contact]).

The original copy of the SAE Report Form and the fax confirmation sheet must be kept with the case report form documentation at the study site.

Follow-up information is sent to the same contact(s) to whom the original SAE Report Form was sent, using a new SAE Report Form stating that this is a follow-up to the previously reported SAE and giving the date of the original report. Each re-occurrence, complication, or progression of the original event should be reported as a follow-up to that event regardless of when it occurs. The follow-up information should describe whether the event has resolved or continues, if and how it was treated, whether the blind was broken or not, and whether the patient continued or withdrew from study participation.

If the SAE is not previously documented in the Investigator's Brochure or Package Insert (new occurrence) and is thought to be related to the Novartis study treatment, an oncology Novartis Drug Safety and Epidemiology (DS&E) department associate may urgently require further information from the investigator for Health Authority reporting. Novartis may need to issue an Investigator Notification (IN), to inform all investigators involved in any study with the same drug that this SAE has been reported. Suspected Unexpected Serious Adverse Reactions (SUSARs) will be collected and reported to the competent authorities and relevant ethics committees in accordance with Directive 2001/20/EC or as per national regulatory requirements in participating countries.

# 7.3 Expedited Reporting to the Food and Drug Administration (FDA)

The Overall PI, as study sponsor, will be responsible for all communications with the FDA. The Overall PI will report to the FDA, regardless of the site of occurrence, any serious adverse event that meets the FDA's criteria for expedited reporting following the reporting requirements and timelines set by the FDA.

# 7.4 Expedited Reporting to Hospital Risk Management

Participating investigators will report to their local Risk Management office any participant safety reports or sentinel events that require reporting according to institutional policy.

# 7.5 Routine Adverse Event Reporting

All Adverse Events **must** be reported in routine study data submissions to the Overall PI on the toxicity case report forms. **AEs reported through expedited processes (e.g., reported to the IRB, FDA, etc.) must** also be reported in routine study data submissions.

# 8. PHARMACEUTICAL AGENT INFORMATION

A list of the adverse events and potential risks associated with the investigational or other agents administered in this study can be found in Section 7.1.

# 8.1 EGF816

The investigator or responsible site personnel must instruct the patient or caregiver to take EGF816 as per protocol. EGF816 will be dispensed to the patient by authorized site personnel only. Dose strength and treatment schedule are described in Table 6-1 and 6-2 and sections 5.3.1 and 5.3.2. All dosages prescribed to the patient and all dose changes during the study must be recorded on the Dosage Administration Record CRF. Study treatment including instructions for administration is dispensed by study personnel. Patients will be provided with adequate supply of EGF816.

8.1.1 EGF816 packaging and labeling

The study medication packaging has a 2-part label. A unique medication number is printed on each part of this label. Responsible site personnel will identify the study treatment package(s) to dispense to the patient by using the IRT and obtaining the medication number(s). Site personnel will add the patient number on the label. All information on labels will be included in the pharmacy reversibility record. Medication labels will be in compliance with the US legal requirements. They will include storage conditions for the drug and the medication number but no information about the patient.

# 8.1.2 EGF816 Supply and storage

EGF816 must be received by designated personnel at the study site, handled and stored safely and properly, and kept in a secured location to which only the investigator and designated site personnel have access. Upon receipt, the study treatment should be stored according to the instructions specified on the drug labels and in the Investigator's Brochure.

# 8.1.3 EGF816 Compliance and Accountability

#### 8.1.3.1 EGF816 Compliance

Compliance will be assessed by the investigator and/or study personnel at each patient visit and information provided by the patient and/or caregiver will be captured in the Drug Accountability Form. This information must be captured in the source document at each patient visit.

## 8.1.3.2 EGF816 Accountability

The investigator or designee must maintain an accurate record of the shipment and dispensing of study treatment in a drug accountability log. Drug accountability will be noted by the field monitor during site visits and at the completion of the study. Patients will be asked to return all unused study treatment and packaging on a regular basis, at the end of the study or at the time of study treatment discontinuation.

At study close-out, and, as appropriate during the course of the study, the investigator will return all used and unused study treatment, packaging, drug labels, and a copy of the completed drug accountability log to the Novartis monitor or to the Novartis address provided in the investigator folder at each site.

## 8.1.4 EGF816 Disposal and Destruction

The study drug supply can be destroyed at the local Novartis facility, Drug Supply group or third party, as appropriate. . IP returned by participants and expired medications will be destroyed at the investigational site.

## 8.2 Gefitinib

Gefitinib will be obtained by each patient through a commercial pharmacy. Patients will be required to bring gefitinib supply in at the start of each treatment cycle for verification by study staff.

## 9. BIOMARKER, CORRELATIVE, AND SPECIAL STUDIES

#### 9.1 **Tumor biopsies**

#### 9.1.1 Pre-treatment biopsy:

Patients will undergo a mandatory fresh core needle or excisional pre-treatment biopsy within 28 days of starting treatment. The site of biopsy will be selected by the treating investigator; cytology specimens and FNA specimens will not be accepted. Cell blocks made from pleural or pericardial fluid are acceptable.At least six cores will be obtained; one fresh sample for single-cell sorting and RNA sequencing, one each for patient-derived cell line and patient-derived xenograft establishment, one core snapfrozen and one core fixed in formalin and embedded in paraffin for subsequent DNA and protein-based studies. An FNA or core sample will be sent for clinical testing to confirm non-small cell histology. Any additional cores will be transported to the MGH Center for Cancer Research at the Charlestown Navy Yard campus.

Although the results of local testing will be used to confirm EGFR mutation status for study screening and registration, all samples will be analyzed centrally post-hoc by NGS for confirmation of pre-treatment EGFR status.

#### 9.1.2 On-treatment biopsy

A mandatory on-treatment core needle or excisional biopsy will be obtained between D15 and 21 of cycle 1. The site of biopsy will be selected by the treating investigator, preferably the same site as the pre-treatment biopsy, however if this is not possible, a biopsy of a different site is allowed; cytology specimens and FNA specimens will not be accepted. Cell blocks made from pleural or pericardial fluid are acceptable. At least four cores will be obtained. One fresh core will be saved in media for single-cell sorting and RNA analysis, one snapfrozen and two cores fixed in formalin and embedded in paraffin for subsequent DNA and protein-based studies. Any additional cores will be sent to the MGH Center for Cancer Research at the Charlestown Navy Yard campus.

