## 1.4 Exploratory Objectives

- To characterize the pharmacokinetic interactions between gefitinib and EGF816.
- To evaluate resistance mechanisms to EGF816 and gefitinib.
- To characterize the molecular response to treatment in on-treatment tumor biopsies and in circulating tumor DNA.

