## 2.5 Correlative Studies Background

## 2.5.1 Pre-treatment, on-treatment and resistant tumor biopsies

Mandatory tumor biopsies will be required at the start of treatment and at the time of disease progression. These samples will be analyzed via next-generation sequencing at Novartis to characterize mechanisms of resistance to the EGF816/gefitinib combination.

In addition, an on-treatment biopsy will be obtained after about 2-3 weeks of treatment. These samples will allow for characterization of the response to treatment. Biopsies will be submitted for single-cell sorting and transcriptional profiling to study the direct effect of the TKI combination on tumor cells, and to identify potential early signs of eventual resistance to the combination. These exploratory analyses will be performed at Massachusetts General Hospital and at Novartis Pharmaceuticals.

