The feasibility of single-cell sorting and transcriptional analysis of on-treatment biopsies will be assessed based on the rate of interpretable results. The lower-bound of the 95% CI will be provided for this rate and will serve as an indication of the ability to use such methods in an expanded setting.

The results of longitudinal ctDNA analysis before, during and after treatment are exploratory and will be evaluated in a descriptive manner.

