#### For each biopsy, cores should be processed in the following order and stored as outlined:

#### 1. Pre-Treatment Biopsy (within 28 days of treatment start)

- 1) Snapfrozen
- 2) Fresh- cell line/PDX (media)
- 3) Fresh- cell line/PDX (media)
- 4) Snapfrozen
- 5) Formalin
- 6) MGH path
- 7) Any extras- snapfrozen

Cores 1-4 (and any extra snapfrozen specimens) to be sent to [name] lab at CNY via courier. Core 5 to be stored in research path by [name]/[name]

Clinical testing- Snapshot, MET and EGFR FISH

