# 2. On-Treatment (C1D15-21)

- 1) Snapfrozen
- 2) Snapfrozen
- 3) Formalin
- 4) Formalin
- 5) Any extra- snapfrozen

Cores 1-2 (and any extra snapfrozen specimens) to be sent to [name] lab at CNY via courier. Cores 3-4 to be stored in research path by [name]/[name]

Note- no MGH path/clinical sample submitted form on-treatment biopsy

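### Section 9.1.2 sets aside one fresh on-treatment core for single-cell sorting, but the Appendix D on-treatment list contains no fresh core

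*Combined protocol and SAP*

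**What the plan says.** Section 9.1.2 makes the on-treatment biopsy (days 15 to 21 of cycle 1) mandatory and asks for at least four cores. It allocates them as "One fresh core will be saved in media for single-cell sorting and RNA analysis, one snapfrozen and two cores fixed in formalin".

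Appendix D gives the handling instructions. Its core lists open with the direction that "cores should be processed in the following order and stored as outlined". The on-treatment list then runs: snap-frozen, snap-frozen, formalin, formalin, with any extra core snap-frozen. Two routing lines follow: "Cores 1-2 (and any extra snapfrozen specimens) to be sent to" the research laboratory, and "Cores 3-4 to be stored in research path by" named staff. The list adds that no on-treatment sample goes for clinical pathology.

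Three other places rely on this biopsy for single-cell work:

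- Section 2.5.1: "Biopsies will be submitted for single-cell sorting and transcriptional profiling to study the direct effect of the TKI combination on tumor cells".
- Section 13.7: "The feasibility of single-cell sorting and transcriptional analysis of on-treatment biopsies will be assessed based on the rate of interpretable results". The lower bound of the 95% confidence interval is to be reported, as an indication of whether the method could be used more widely.
- Section 1.4, where the related objective is exploratory: "To characterize the molecular response to treatment in on-treatment tumor biopsies and in circulating tumor DNA".

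**The concern.** The fresh core in Section 9.1.2 is the one assigned to single-cell sorting. Appendix D is the operational text and leaves it out. A team that follows Appendix D to the letter will freeze or fix every on-treatment core, and that choice cannot be reversed after collection.

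What is at stake is the feasibility rate in Section 13.7. If everyone follows Appendix D, the rate has no specimens of the type the protocol body describes. If practice is mixed, the rate partly measures which instruction was followed and not whether the method works. Patients also undergo this biopsy for research only: willingness to have it is a condition of entry (criterion 3.2.5), and Appendix D sends none of it for clinical testing. The specimen it is taken for should therefore be specified consistently.

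**Working it through.** The check is a count of cores by type in the two texts.

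**On-treatment biopsy**

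| Core type | Section 9.1.2 | Appendix D |
|---|---|---|
| Fresh in media, single-cell | 1 | 0 |
| Snap-frozen | 1 | 2 |
| Formalin | 2 | 2 |
| Total | 1 + 1 + 2 = 4 | 0 + 2 + 2 = 4 |
| Extra cores | sent to the research centre, type not stated | snap-frozen |

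The totals agree with the stated minimum of four. The single difference is that the fresh core has become a second snap-frozen core.

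**Could the texts be read as agreeing?**

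1. *Notation.* Appendix D labels cores as fresh in its pre-treatment and post-progression lists, and adds the medium in the former. It uses the label where it wants it, and the on-treatment list does not have it.
2. *Extra cores.* Appendix D freezes these too, so they do not supply the missing core.
3. *Routing.* Cores 1-2 and any extras go to the laboratory and cores 3-4 to research pathology. No core is left unassigned.

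**Pre-treatment and post-progression biopsies (secondary)**

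Sections 9.1.1 and 9.1.3 ask for "one fresh sample for single-cell sorting and RNA sequencing, one each for patient-derived cell line and patient-derived xenograft establishment", plus one snap-frozen, one formalin and one clinical sample.

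| Core type | Sections 9.1.1 and 9.1.3 | Appendix D |
|---|---|---|
| Fresh, single-cell | 1 | 0 |
| Cell line / xenograft | 2 | 2 |
| Snap-frozen | 1 | 2 |
| Formalin | 1 | 1 |
| Clinical pathology | 1 | 1 |
| Total | 6 | 6 |

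The same substitution appears. It matters less here, because two fresh cores remain and Section 13.7 plans no feasibility rate at these time points. Section 13.7 does, however, include single-cell RNA sequencing among the comparative analyses of pre-, on- and post-treatment biopsies.

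**Effect on the feasibility rate**

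Let *f* be the share of on-treatment biopsies handled as in Section 9.1.2, *p* the probability of an interpretable result from a fresh core, and *q* the probability from a snap-frozen core. The expected rate over all biopsies is

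f × p + (1 − f) × q.

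- If everyone follows Section 9.1.2, f = 1 and the rate estimates p.
- If everyone follows Appendix D, f = 0 and the rate estimates q. If frozen tissue cannot be used, q = 0.
- If practice is mixed, the rate depends on f unless p = q.

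The available text gives none of f, p or q, so the size of any distortion cannot be calculated. The number of patients with a core of the Section 9.1.2 type runs from 0 × 36 = 0 to 1 × 36 = 36 at full planned enrolment, or from 0 to 11 for stage 1 alone.

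**The case against.** The mismatch itself is hard to dispute, but four objections bear on its weight.

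- *Unseen text.* A portion of the document immediately before the Appendix D core lists was not available for this review and might explain how the single-cell core is handled. This stands as a limit: it can only be said that the available text does not state which instruction prevails. The on-treatment list itself is complete.
- *Frozen tissue may be adequate.* Nothing available says whether the assay can run on a snap-frozen core. If it can, the rate can still be produced and the fault lies in the wording of Section 9.1. This also stands, and is why the fix starts with the laboratory. Even then, the rate would describe a different specimen from the one the protocol body names.
- *Exploratory status.* The rate has no threshold and drives no trial decision. This is correct and limits the seriousness, but single-cell work is still the stated purpose of a mandatory biopsy.
- *The range is only a bound.* From 0 to 36 is simply none to all. It assumes that every patient reaches the biopsy and yields cores, and Section 13.7 does not say whether the six extra patients treated after a de-escalation count within the 36. Mixed practice is likewise a possibility and not something the documents show. The firm figure is 1 against 0 fresh cores out of four.

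**Conclusion.** The two texts contradict each other. Section 9.1.2 requires one fresh core of four for single-cell sorting; Appendix D provides none of four and freezes any extra. Followed as written, Appendix D leaves no specimen of the specified type for the work described in Section 2.5.1 or for the rate in Section 13.7.

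The contradiction is certain from the text. Its effect on the rate is not, because that depends on which instruction staff follow and on whether frozen tissue suits the assay. The snap-frozen and formalin cores remain usable for DNA, protein and bulk analyses. The correction should be made because it is cheap and a missed fresh core cannot be replaced, but it has no bearing on the trial's main conclusions.

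**What to change.** Before further biopsies are collected, confirm with the laboratory which specimen its single-cell assay uses, then make one of two changes.

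- **(a) If the assay needs fresh tissue:** in the Appendix D on-treatment list, replace one snap-frozen core with a fresh core in media marked for single-cell sorting. Do the same in the pre-treatment and post-progression lists. Core counts stay at four and six. The cost is one snap-frozen core per biopsy and a wording change in Appendix D.
- **(b) If the assay uses frozen tissue:** amend Sections 9.1.1 to 9.1.3 to match Appendix D, and define the Section 13.7 feasibility rate for snap-frozen specimens. The cost is wording in those sections.

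Neither option adds a core or a procedure. If biopsies have already been collected, record the specimen type for each and report the rate by type.
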